## 10.7 Initial Follow-up Visit

### 10.7.1 Pralatrexate Arm

All patients who receive at least 1 dose of pralatrexate will attend the Initial Follow-up Visit 35 ( $\pm$  5) days after the last dose of pralatrexate.

In the event the patient withdraws consent to any further study participation and refuses to attend the Initial Follow-up Visit, the following procedures and evaluations must be performed at the time the patient withdraws consent.

1. Record concomitant medications through 30 days after the last pralatrexate dose.
2. Record all AEs and attribution through 30 days after the last pralatrexate dose. From 31 days after the last pralatrexate dose, only record pralatrexate-related AEs and attribution (see <http://ctep.cancer.gov/reporting/ctc.html>).
3. Assess and record B symptoms.
4. Perform physical examination. Document any new or worsened findings as AEs.
5. Assess and record ECOG performance status (see [Appendix 3](#)).
6. Local laboratory: collect blood for hematology and serum chemistry (including LDH, see [Section 12.1](#)).
7. Review dosing of folic acid and document compliance.
8. Instruct patient to discontinue folic acid and vitamin B12.
9. Record reason for discontinuation of pralatrexate ([Section 11.1](#)).
10. Record first subsequent therapy for PTCL, if applicable.

### 10.7.2 Observation Arm

Patients who are randomized to the Observation Arm will attend the Initial Follow-up Visit 35 days ( $\pm$  5 days) after study treatment discontinuation criteria are met.

In the event the patient withdraws consent to any further study participation and refuses to attend the Initial Follow-up Visit, the following procedures and evaluations must be performed at the time the patient withdraws consent.

1. Record concomitant medications through 30 days after study treatment discontinuation criteria ([Section 11.1](#)) are met.
2. Record all AEs and attribution (see <http://ctep.cancer.gov/reporting/ctc.html>) through 30 days after study treatment discontinuation criteria ([Section 11.1](#)) are met.
3. Assess and record B symptoms.

4. Perform physical examination. Document any new or worsened findings as AEs.
5. Assess and record ECOG performance status (see [Appendix 3](#)).
6. Local laboratory: collect blood for hematology and serum chemistry (including LDH, see [Section 12.1](#))
7. Review dosing of folic acid and document compliance.
8. Instruct patient to discontinue folic acid and vitamin B12.
9. Record reason for discontinuation of observation ([Section 11.1](#)).
10. Record first subsequent therapy for PTCL, if applicable. First subsequent therapy for PTCL is at the investigator's discretion and can include pralatrexate.

## 10.8 Follow-up Visits

All patients who are randomized are to have follow-up as outlined below until objectively documented PD; thereafter, patients are followed for survival. The timing of follow-up will be at 8 weeks ( $\pm 1$  week), then every 12 weeks ( $\pm 1$  week) through 3 years post-randomization, and then every 24 weeks ( $\pm 4$  weeks) thereafter through 7 years post-randomization. PD will be confirmed by central review until the first PFS analysis, see [Section 15.6.1](#), and per investigator assessment thereafter.

The following procedures/evaluations must be performed at each follow-up time point.

1. Record study-treatment-related AEs (see <http://ctep.cancer.gov/reporting/ctc.html>).
2. Evaluation of response (see [Section 10.6](#) for tests and procedures).
3. Record subsequent therapies for PTCL and document the best response to the first subsequent therapy.

## 10.9 Long-term Follow-up

All subsequent therapies for PTCL will be collected for up to 7 years from randomization and the best response to the first subsequent therapy will be documented. Once patients have documented PD, survival status and subsequent therapies will be collected on all patients approximately every 6 months through 7 years from randomization.

## 11 DURATION OF TREATMENT

All patients are free to withdraw from participation in this study at any time, for any reasons, specified or unspecified, and without prejudice. The reason for the patient discontinuing pralatrexate/observation or terminating from the study must be recorded on the case report form (CRF). Pralatrexate will continue to be administered until a criterion for study treatment discontinuation is met ([Section 7.3](#)) or up to a maximum of 2 years.

### 11.1 Criteria for Study Treatment Discontinuation

Patients will receive study treatment (pralatrexate or observation) until one of the following criteria for study treatment discontinuation applies:

- Development of PD
- Initiation of RT or systemic chemo/biological therapy for treatment of PTCL
- Receipt of systemic steroids > 10 days, with the exception of those as stated in exclusion criterion #5 (see [Section 8.4](#))
- Development of an AE that interferes with the patient's participation
- Lost to follow-up
- Patient decision
- Investigator decision
- Sponsor decision

In addition, for those patients randomized to the Pralatrexate Arm, additional pralatrexate treatment discontinuation criteria are:

- 3 or more consecutive doses of pralatrexate omitted or more than 28 days between doses of pralatrexate
- Treatment with pralatrexate for 2 years

Patients will be seen for the Initial Follow-up Visits as outlined in [Section 10.7](#).

If an investigator feels that a patient would continue to benefit from pralatrexate therapy after completion of 2 years' therapy, they should discuss with the sponsor's medical contact and agree whether or not it is appropriate to continue treatment.

## **12 LABORATORY TESTS**

### **12.1 Local Laboratory Tests**

The following panels will be done locally with the designated tests. Copies of current laboratory certifications and normal ranges will be provided to Allos at study start and upon every renewal throughout the duration of pralatrexate or observation for the longest participating patient at the site.

#### **12.1.1 Hematology**

Tests to be conducted are white blood cell (WBC) count, hemoglobin (Hgb) concentration, hematocrit (Hct), platelet count, and ANC.

#### **12.1.2 Chemistry**

Tests to be conducted are creatinine, total bilirubin, AST, ALT, LDH, total protein, albumin, and  $\beta$ -hCG pregnancy test at screening (if applicable).

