## 14 ADVERSE EVENTS

### 14.1 Definition

An AE is defined as any untoward medical occurrence in a patient or clinical investigation patient, temporally associated with the use of a medicinal product, whether or not considered related to the medicinal product. Therefore, an AE can be any unfavorable and unintended sign (including an abnormal laboratory finding), symptom, or disease (new or exacerbated) temporally associated with the use of a medicinal product. This definition of an AE will be extended in this study to include any untoward medical occurrence in patients participating in the Observation Arm of the study, as well.

The term “toxicity” is not clearly defined by regulatory organizations and is currently used only for historical reasons by the NCI. Therefore, the term “adverse event” is used throughout this document to refer to any unfavorable and unintended sign (including an abnormal laboratory finding), symptom, or disease temporally associated with the study drug, as well as any other study-treatment-related toxicities. However, since this is an investigational study, all toxicities are considered AEs and must be reported.

Examples of an AE **include**:

- Exacerbation of a chronic or intermittent pre-existing condition including either an increase in frequency and/or intensity of the condition.
- New conditions detected or diagnosed after investigational product administration, even though it may have been present prior to the start of the study.
- Signs, symptoms, or the clinical sequelae of a suspected drug interaction.
- Signs, symptoms, or the clinical sequelae of a suspected overdose of either investigational product or a concurrent medication.
- AEs may include pre-treatment or post-treatment events that occur as a result of protocol-mandated procedures (ie, invasive procedures, modification of patient’s previous therapeutic regimen).

Examples of an AE **do not include** a/an:

- Medical or surgical procedures (eg, endoscopy, appendectomy); the condition that leads to the procedure is an AE.
- Situations where an untoward medical occurrence does not occur (eg, social and/or convenience admission to a hospital).
- Anticipated day-to-day fluctuations of pre-existing disease(s) or condition(s) present or detected at the start of the study that do not worsen.

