### 14.3 Recording of Adverse Events

#### 14.3.1 Recording of Adverse Events

Any AE that occurs from the time the study IC is obtained until randomization needs to be recorded on the AE CRF page(s), **only** if the event was related to a study procedure. All other AEs/findings prior to randomization must be recorded as baseline findings on the applicable CRF page(s).

Any AE that occurs from randomization through 30 days after the last dose of pralatrexate or through 30 days after treatment discontinuation criteria are met for the Observation Arm must be recorded on the AE CRF. From 31 days after the last dose of pralatrexate, only AEs that are related to pralatrexate need to be captured on the AE CRF.

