PFS time is calculated as the number of days from randomization to the date of objective documentation of PD or death, regardless of cause (PD date/death date - date of randomization + 1). Patients who are alive without a disease response assessment of PD will be censored at their last disease assessment date or the date of randomization, whichever is later. Date of progression will not be imputed for patients with missing tumor assessment(s) before an assessment of PD. Patients who withdraw from treatment prior to PD without withdrawing consent will be followed for disease status whenever possible, even if subsequent therapy, including transplant, has been initiated prior to documented PD per central review at least until the first interim analysis. Patients who have not died and who have no response assessments after baseline will be censored at randomization.

Overall Survival Time

OS time is calculated as the number of days from randomization to death (date of death - date of randomization + 1). Patients who have not died (no record of death) or are lost to follow-up will be censored at the date of last contact. Patients who withdraw from study visit participation will be followed for survival status. OS will be reported in months.

Treatment-emergent Adverse Event

A treatment-emergent AE is defined as an AE that occurs on or after study day 1 and that is a higher grade than was present just prior to study day 1.

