8.6 Safety Analyses

Analysis of safety will be performed on the safety analysis set. Study data will be monitored on an ongoing basis by the clinical study team including the medical monitor and the clinical drug safety team's routine activities to ensure patients' safety.

Adverse Events

The Medical Dictionary for Regulatory Activities (MedDRA) will be used to code all AEs to a system organ class (SOC) and a preferred term. Patient incidence of AEs will be tabulated by SOC, preferred term, and severity grade for all treatment-emergent AEs, serious adverse events (SAEs), treatment-related AEs, and treatment-related SAEs. Each of these outputs will include tabulation by maximum severity for each SOC and preferred term as reported by the investigator based on Common Terminology Criteria for Adverse Events (CTCAE),

Version 4.0. If an AE cannot be graded based on CTCAE, the investigator will assign a severity based on 1 = mild, 2 = moderate, 3 = severe, 4 = life threatening, and 5 = Death related to AE. Summaries of AEs that are treatment-emergent, SAEs, treatment-related AEs, and treatment-related SAEs occurring in at least 5% of the patients will be provided in descending order of frequency by SOC and preferred term.

Additional tables summarizing patient incidence (by preferred term) of the following will be generated:

- All AEs;
- SAEs;
- Treatment-related AEs;
- Treatment-related SAEs;
- Grade 3 or higher AEs;
- AEs leading to the discontinuation of pralatrexate or removal from study;
- AEs leading to dose reductions of the study drug;
- AEs with incidence $\geq 5\%$; and
- Deaths.

Adverse Events Grouped by Similar Preferred Term

Summary tables of treatment emergent, treatment-related, serious, and serious treatment-related AEs grouped by similar preferred term will be presented. For this presentation, certain similar preferred terms were identified and coded to the same preferred term in order to present the event in a uniform manner. Terms are presented in [Table 11.1](#) of Appendix 11.4 (additional preferred terms may be identified within each category during data review and added to this list).

Separate outputs will be provided for subgroups defined by age group (< 65 and ≥ 65), gender, and race (if feasible).

Detailed listings for all AEs and listings and/or narratives will be provided for serious and significant AEs and deaths (with “on-study” deaths [deaths that occur before the end of safety follow-up period] identified).

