Overall Summary of Treatment Emergent AEs – Safety Analysis Set	High-level summary of treatment-emergent, serious, treatment-related, and serious treatment-related AEs. Only include treatment-emergent AEs (this applies to all AE tables).
Treatment-emergent AEs – Safety Analysis Set	Summary by SOC and preferred term for each treatment group.
Treatment-emergent AEs Grouped by Similar Preferred Term – Safety Analysis Set	Summary by preferred term for each treatment group, where selected AEs are grouped by similar preferred term as indicated in the appendix.
Treatment-emergent SAEs – Safety Analysis Set	Summary by SOC and preferred term for each treatment group.
Treatment-emergent SAEs Grouped by Similar Preferred Term – Safety Analysis Set	Summary by preferred term for each treatment group, where selected AEs are grouped by similar preferred term as indicated in the appendix.
Treatment-emergent AEs Grouped by Similar Preferred Term Leading to Treatment Discontinuation – Safety Analysis Set – Pralatrexate Arm	Summary by preferred term.
Treatment-emergent AEs by Age Group – Safety Analysis Set	Summary by SOC and preferred term for each age group (< 65, ≥ 65).
Treatment-emergent AEs by Gender – Safety Analysis Set	Summary by SOC and preferred term for each gender.
Treatment-emergent AEs by Race – Safety Analysis Set	Summary by SOC and preferred term for each race (if feasible).
Time to worsening of B-symptoms/Pruritus – Safety Analysis Set	Analysis using the Cox model of time to worsening of B-symptoms/pruritus.
Hematology – Safety Analysis Set	Summary of hematology parameters at baseline, last observed value, maximum observed value, and minimum observed value. Include change from baseline to maximum observed value, minimum observed value and last observed value.
Hematology Shift in Severity – Safety Analysis Set	Tables of shifts in severity from baseline for selected laboratory parameters and selected time points.
Serum Chemistry – Safety Analysis Set	Summary of serum chemistry parameters at baseline, last observed value, maximum observed value, and minimum observed value. Include change from baseline to maximum observed value, minimum observed value, and last observed value.

Title	Description
Chemistry Shift in Severity – Safety Analysis Set	Tables of shifts in severity from baseline for selected laboratory parameters and selected time points.

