11.4 Preferred Terms for Adverse Events Grouped by Similar Preferred Term

Listed in Table 11.1 below are the AEs identified for the pralatrexate program. The AEs grouped by similar preferred term are evolving over time as the coding dictionary is updated (there could be changes to the already identified events) and as the pralatrexate program expands (additional AEs may be added and others may be removed). AEs included in the data summary will be based on the current list identified by the clinical study team at the time of the analysis.

Table 11.1. Adverse Events Grouped by Similar Preferred Term

Category	Preferred Term
Mucosal Inflammation	Mucosal inflammation Stomatitis Anal Inflammation Mucositis Anal Vaginal Inflammation Rectal Mucositis Esophagitis Mouth Ulceration Oral Mucosal Erythema Oesophagitis Gingivitis Balanoposthitis Pharyngeal Inflammation Pharyngitis Stomatitis Haemorrhagic
Thrombocytopenia	Thrombocytopenia Platelet Count Decreased
Anemia	Anemia Hemoglobin Decreased
Hypokalemia	Hypokalemia Blood Potassium Decreased
Neutropenia	Neutropenia Neutrophil Count Decreased
Dermatitis Exfoliative	Dermatitis Exfoliative Exfoliative Rash
Rash	Rash Dermatitis Acneiform Rash Maculo-papular Rash Macular Rash Papular Dermatitis

Category	Preferred Term
	Dry Skin Rash Erythematous Skin Disorder
Liver Function Test Abnormal	Liver Function Test Abnormal Alanine Aminotransferase Increased Alanine Aminotransferase Aspartate Aminotransferase Aspartate Aminotransferase Increased Transaminases Increased
Oedema	Oedema Oedema Peripheral Pitting Oedema
Dry Mouth	Dry Mouth Lip Dry Dry Throat
Dyspepsia	Dyspepsia Gastritis Gastrooesophageal Reflux Disease
Odynophagia	Odynophagia Oesophageal Pain
Pruritus	Pruritus Pruritus Generalized
Anorexia	Anorexia Decreased Appetite
Leukopenia	Leukopenia White Blood Cell Count Decreased

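### Hypokalemia is set up as a grouped adverse event tabulated by arm, but no scheduled laboratory panel measures potassium, so asymptomatic cases are likely to be under-detected

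*Protocol*

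**What the plan says.** Protocol 12.1 states that "The following panels will be done locally with the designated tests". Section 12.1.1 then names white cells, hemoglobin, hematocrit, platelets and neutrophils. Section 12.1.2 names the chemistry tests: "Tests to be conducted are creatinine, total bilirubin, AST, ALT, LDH, total protein, albumin", with a pregnancy test at screening where applicable.

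SAP 11.4, Table 11.1, has a row that reads "Hypokalemia Blood Potassium Decreased", meaning that the second and third words onward are preferred terms merged under the hypokalemia category. SAP 8.6 commits to the output: "Summary tables of treatment emergent, treatment-related, serious, and serious treatment-related AEs grouped by similar preferred term will be presented". The corresponding entry in SAP Table 9.1 is specified as "Summary by preferred term for each treatment group, where selected AEs are grouped by similar preferred term as indicated in the appendix". Protocol 15.8.2 makes the same commitment and refers to the SAP for the terms.

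**The concern.** The analysis plan has a reporting line for a laboratory-defined event that the data collection plan does not set out to measure. A low potassium without symptoms reaches the database only if a site happens to order the test and then reports the result. A low count in the by-arm table could then reflect little testing as easily as few events.

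The comparison between arms is also exposed. The trial is open-label and contact is unequal. Patients on pralatrexate have blood taken before each of three doses per 4-week cycle (protocol 10.4.2 and 10.4.3). Patients on observation have one laboratory visit every 28 days, plus a week-2 contact that may be a telephone call (10.5.2 and 10.5.3). Discretionary testing could differ by arm for reasons unrelated to how often potassium falls. Safety is the only secondary objective, although it does not rest on this one row.

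**Working it through.** The plan states no figure on this point, so the check sets the sections side by side.

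**1. Is potassium scheduled anywhere?**
- Hematology panel (protocol 12.1.1): no.
- Chemistry panel (12.1.2): no.
- Laboratory visits in both arms (10.1, 10.4.1 to 10.4.3, 10.5.1, 10.5.3, 10.7.1, 10.7.2): all call for hematology and chemistry and add no electrolyte.
- Central laboratory (12.2.1): plasma is used for pralatrexate concentration only. The rest of 12.2 covers pathology, photography and imaging.

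Result: 0 scheduled potassium values per patient in either arm.

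**2. Is this true of the other laboratory-defined groups?** Six rows of SAP Table 11.1 are defined by a laboratory value (my classification):

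| Group | Scheduled test |
|---|---|
| Thrombocytopenia | Platelets (12.1.1) |
| Anemia | Hemoglobin (12.1.1) |
| Neutropenia | ANC (12.1.1) |
| Leukopenia | WBC (12.1.1) |
| Liver function test abnormal | AST, ALT (12.1.2) |
| Hypokalemia | None |

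Five of six have a scheduled test; hypokalemia alone has none.

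**3. Could the laboratory tables make up for it?** SAP 8.6 plans Grade 3 or 4 laboratory incidence and severity shifts, and SAP 11.2 derives laboratory grades by program. Both work from collected laboratory values, and no potassium values are planned. Reported adverse events are therefore the only planned source.

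**4. What can be said about size?** Write p for the true incidence in an arm and s for the share of cases detected. The observed incidence is s × p, and the observed difference is s₁p₁ − s₀p₀, with 1 for pralatrexate and 0 for observation. The documents give neither p nor s, so the values below are assumptions used only to show the range.

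- Equal detection, true incidence 15% against 5%. The observed difference is s × 10 points: 10.0, 7.5, 5.0 and 2.5 points at s = 100%, 75%, 50% and 25%.
- Equal detection, true incidence 10% against 3%. The observed difference is s × 7 points: 7.0, 5.25, 3.5 and 1.75 points at the same values of s.
- Unequal detection, true incidence 10% in both arms. With s₁ = 75% and s₀ = 25%, the observed difference is 7.5 − 2.5 = +5.0 points. With the shares reversed it is 2.5 − 7.5 = −5.0 points.

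Equal under-detection shrinks a real difference. Unequal under-detection can create one in either direction. Nothing in the documents says which applies, or how strongly.

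**The case against.** The strongest reply is that Table 11.1 is a coding device. It ensures that two terms for one event are counted together. It covers the whole pralatrexate program and may be revised before analysis. A row in it does not promise a scheduled assessment, any more than the oedema row does. The precautions in protocol 4.3.1 do not mention hypokalemia, no eligibility or dose-modification rule uses potassium, and the documents give no incidence. This stands as a limit on weight: the row is not a declared event of special interest. It does not remove the gap, because the current SAP lists the event and plans to tabulate it, and its laboratory-defined neighbours are all measured.

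A second reply is that reporting routes exist. The protocol's definition of an adverse event covers "any unfavorable and unintended sign (including an abnormal laboratory finding), symptom, or disease", and events are reviewed at regular contacts in both arms. This also stands. Detection is incomplete and unstandardized, not absent. A reader might infer from 12.1 that sites may not measure potassium; the section says what the panels contain and does not bar further local tests.

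A reader might also infer that treatment-emergent status cannot be settled, because the SAP requires an event "that is a higher grade than was present just prior to study day 1" and no pre-treatment potassium is planned. The documents do not support that. Adverse event grades come from the investigator (SAP 11.2), and known earlier abnormalities have a place: "All other AEs/findings prior to randomization must be recorded as baseline findings". An event can be classified without a protocol-scheduled laboratory value.

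**Conclusion.** The point holds as a minor one. Potassium is not scheduled in either arm, while hypokalemia is planned for by-arm tabulation and is the only one of six laboratory-defined groups in that position. Under-detection of asymptomatic cases is likely. That judgment assumes that sites do not all measure potassium routinely and report every low value, which the documents do not say either way.

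A reader might go further and conclude that the safety comparison is biased for or against pralatrexate. Unequal contact and open-label care make an imbalance possible, but its existence, size and direction cannot be derived. The adverse event tables are descriptive. No dosing rule depends on potassium, and PFS, OS, sample size and alpha are untouched.

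**What to change.** Add potassium to the chemistry panel in protocol 12.1.2, run on blood already being drawn:
- at screening;
- at cycle 1 dose 1, or the observation baseline visit;
- every 4 weeks in both arms, at dose 1 of each later cycle and at the 28-day observation visit, which is the timing already used for LDH;
- at the Initial Follow-up Visit.

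Include it in the laboratory summaries of SAP 8.6, with CTCAE grading under SAP 11.2. If a potassium grade turns on a clinical assessment, 11.2 already excludes it from derivation by program, and the planned summaries of minimum, last and change values would still show the result.

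The cost is one routine local analyte and one data field at each of these visits. A SAP sentence saying that hypokalemia is ascertained only from reported events would be honest, but on its own it records the limitation without improving detection or patient monitoring.
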